**14.5. APPENDIX 5 - ACCEPTABLE TIME WINDOWS FOR ASSESSMENTS/ PROCEDURES**

Assessment/Procedure	Window
Investigational Product administration	
Start of Investigational Product infusion @ 12hrs prior to islet transplant.	6-18hrs prior to start of islet infusion
End of Infusion @ 7 days (168hrs).	± 12hrs
Follow-up visits	
Visit @ day 75 and 365 after the transplant	± 14 days
Mixed Meal Tolerance Test	
Sampling @ 15, 30, 60, 90, 120, 180, 240 mins after the meal	± 5 mins (15 min and 30 min) or ± 10 mins (60 to 240 min)
Chemokine/cytokines; miR-375	
Sampling @ 6, 12, 24, 72, 120 and 168hrs after islet infusion	± 10 mins (6 to 24 hrs) or ± 30 mins (72 to 168hrs)
PK sampling	
Sampling on post-operative day 1, 3 and 5, ideally in the morning	Between 5.30 a.m. and 12.30 p.m.
Sampling just prior to termination of Investigational Product administration	Within 6 hrs before the end of Investigational Product administration
Sampling @ 1, 3, 5, 6, 8, and 12 hrs after termination of Investigational Product administration	± 10 mins

## 14.6. APPENDIX 6 - METHODOLOGICAL DETAILS

### 14.6.1. Islet determination

The following method will be used to quantify isolated and infused IEQ.

After staining dithizone, islets will be counted by phase contrast microscope and grouped in classes according to their size (islet diameter;  $\mu\text{m}$ ). IEQ will be derived from the islet number in each class integrated by a conversion factor, as detailed in the table below, where “n” is the number of islet in each class.

Class [islet diameter range ( $\mu\text{m}$ )]	Conversion into IEQ [islets of 150 $\mu\text{m}$ diameter]
50-100	n / 6
101-150	n / 1.5
151-200	n x 1.7
201-250	n x 3.5
251-300	n x 6.3
301-350	n x 10.4
>350	n x 15.8

### 14.6.2. Calculation of creatinine clearance

Renal function will be evaluated by creatinine clearance (CLcr), calculated by the following formula (Cockcroft-Gault, 1976):

$$\text{Male: CLcr} = \frac{[140 - \text{age (years)}] \bullet \text{Weight (kg)}}{\text{Serum Creatinine (mmol / L)} \bullet 815}$$

$$\text{Female: CLcr} = \frac{[140 - \text{age (years)}] \bullet \text{Weight (kg)}}{\text{Serum Creatinine (mmol / L)} \bullet 815} \bullet 0.85$$

### 14.6.3. Handling of samples for centralized assays and assay methods

Detailed instructions will be provided for preparation, storage and shipment of samples. Tubes and labels for storage will be provided by the CRO appointed by Dompé, along with storage and shipment tracking forms.

Samples will be shipped in appropriate package in dry ice (solid  $\text{CO}_2$ ) to maintain frozen conditions. All samples will be shipped on an ongoing basis during the trial, according to logistics. However, samples from the last patient visits will be shipped as soon as possible to ensure timely availability of results.

Arrangements will be made with each centralized laboratory to provide appropriate procedures for receipt and analysis of the samples and, apart from PK analysis (see section “PK samples below”), back-communication of the results to the sending site. All steps will be tracked to ensure correct data reporting.

Once received from the centralized laboratory, each site will enter values pertaining to its patients in the corresponding CRF. All samples will be destroyed after final study report has been issued or after the patient has withdrawn his/her consent.

The centralized laboratory for the assay of C-Peptide, HbA1c and Inflammatory chemokines/cytokines will be:

Northwest Lipid Metabolism and Diabetes Research Laboratories ([name]., D.Sc.); University of Washington - [name] - US. [contact]; [contact]. The laboratory is certified by CLIA and all the analyses are performed under strict quality control. Also, the laboratory participates in the National Glycohemoglobin Standardization Program (NGSP) and the method is yearly certified at the level of Laboratory 1 Certification to ensure that the HbA1c values are traceable to the DCCT values.

The centralized laboratory for the assay of miR-375 will be:

Diabetes Research Institute, β-cell Biology Unit ([name]); IRCCS Ospedale San Raffaele; [name].

The centralized laboratory for the assay of PK samples will be:

CDMO Department ([name] BSc), Quality Control Laboratory; Dompé s.p.a. - [name]. [contact]; e-mail: [contact]

▪ C-peptide

Blood samples will be kept at room temperature for at least 30 min to allow clotting. They will then be centrifuged at  $700 \times g$  within one hour from sampling. Cell free serum samples for each time-point will be aliquoted (at least 2 x 0.5mL aliquots) and stored between -70°C and -80°C until shipment to the centralized laboratory. Determination of C-peptide levels will be performed by a two site immuno-enzymometric assay using a Tosoh 2000 auto-analyzer (TOSOH, Biosciences, Inc., South San Francisco, CA).

▪ HbA1c

EDTA whole blood samples will be collected and at least 2 x 1 mL aliquots will be stored between -70°C and -80°C until shipment to the centralized laboratory. Measurement of the relative proportion of hemoglobin subclasses and calculation of the HbA1c levels are performed by a dedicated analyzer (TOSOH, Biosciences, Inc) using non-porous ion exchange high performance chromatography to achieve rapid and precise separation of stable HbA1c from other hemoglobin fractions.

▪ Inflammatory chemokines/cytokines

Blood samples, obtained before (2 basal samples collected 6 to 24 hrs apart; both samples will be obtained before surgery and before Investigational Product administration is started) and 6, 12, 24, 72, 120 and 168hrs after the end of islet infusion, will be immediately kept at 4°C, protected from the light and centrifuged within 2 hrs at  $700 \times g$  at 4°C. Cell free serum will be aliquoted (4 x 100µL aliquots) and stored between -70°C and -80°C until shipment to the centralized laboratory and analysis.

Starting from 25µL of thawed serum the following chemokines/cytokines will be determined by a multiplex technology that uses magnetic bead sets (BioRad BioPlex instrument using a Human Cytokine Panel; Millipore Inc., HCYTOMAG-60K): CXCL8, CCL2 (MCP-1), CCL3, CCL4, CXCL10 (IP-10), IL-6, IL-10, INF-γ, TNF-α, and IL-1β. Due to cross-reactivity with the Human Cytokine Panel (HCYTOMAG-60K), analysis of CXCL-9 (MIG) is performed on a BioRad BioPlex system using MILLIPLEX MAP Human Cytokine/Chemokine Magnetic Bead Panel III (Millipore, Inc., HCYP3MAG-63K).

▪ miR-375

Blood samples, obtained before (one basal sample collected before surgery and before Investigational Product administration is started) and 6, 12, 24, 72, 120 and 168hrs after the end of islet infusion, will be immediately kept at 4°C, protected from the light and centrifuged within 2 hrs at  $700 \times g$  at 4°C. Cell free

serum samples for each time-point will be aliquoted (at least 2 x 300 $\mu$ L aliquots) and stored between -70°C and -80°C until shipment to the centralized laboratory and analysis.

Circulating miR-375 levels will be measured by droplet digital PCR (ddPCR); serum samples will be extracted with commercially available kits and the recovered miRNA fraction will be first reverse transcribed and then partitioned into approximately 20000 droplets using the droplet generator of the Bio-Rad QX100 droplet digital PCR system. After PCR amplification in a conventional thermal cycler, each individual droplet from each sample will be read and its fluorescent status assessed using the QX100 droplet reader. The output of the QX100 reader will be analyzed using the QuantaLife 1.3 software.

▪ PK samples

Blood samples will be taken into lithium heparin monovettes and centrifuged ideally within 15 minutes at 2500 x g at 4°C for 10 minutes. If that is not possible then samples can be stored at room temperature for not more than 2 hours or at 4°C for not more than 24 hours before centrifugation. Plasma will be aliquoted (2 x 1.5mL aliquots) and stored at a temperature in the range -20°C to -80°C into stopped tubes (glass or plastic), until shipment to the centralized analytical laboratory.

Analaysis will be carried out within one year from sampling. i.e. before the study blind is broken. Therefore, all samples obtained during the conduct of the trial will be sent to the centralized laboratory and analyzed in order to maintain the study blind. Appropriate procedures will be implemented by the centralized laboratory to guarantee the blinding; also, results will be released only after study blind has been broken.

Analysis will be performed according to standardized and validated methods as per Good Laboratory Practices. In particular, the following PK parameters will be determined:

$C_{initial}$	Plasma concentration of reparixin and metabolites (DF 2243Y and ibuprofen) just prior to the end of infusion;
$C_{max}$	Maximum plasma concentration of reparixin and metabolites;
$t_{max}$	Time of maximum plasma concentration reparixin and metabolites;
$\lambda_z$	Terminal phase rate constant of reparixin and metabolites;
$t_{1/2}$	Terminal half life of reparixin and metabolites;
$AUC_{0-t}$	Area under the plasma concentration-time curve from time zero ( $C_{initial}$ ) to time t (time of last quantifiable plasma concentration) of reparixin and metabolites;
$AUC_{0-\infty}$	Area under the plasma concentration-time curve from time zero ( $C_{initial}$ ) to infinity of reparixin and metabolites
$V_z$	Volume of distribution of reparixin
$CL$	Clearance of reparixin

Data will be summarised in a separate report that will be integrated into the final study report.

#### 14.6.4. Mixed Meal Tolerance Test

The MMTT will be performed on all patients possibly after an overnight fast, according to Greenbaum (2008). The test will be initiated before 10 a.m. The Boost High Protein will be used for the MMTT.

Patients will be given 6mL/kg of Boost preparation up to a maximum of 360mL, to be drunk within 5 min. Blood samples for glucose, C-peptide and insulin measurement will be withdrawn in basal condition (two samples in the range between -20 to 0 prior to the meal) and then @ 15, 30, 60, 90, 120, 180 and 240 min after the meal.

**14.6.5. β-score calculation**

**β-score** will be calculated on a 0-8 scoring system (Ryan, 2005) which gives 0-2 points each for glucose, HbA1c, stimulated C-peptide and insulin requirement, as per the table below.

Components	Score 2	Score 1	Score 0
Fasting (or before breakfast) plasma glucose (mg/dL OR mmol/L)	$\leq 99$ OR $\leq 5.5$	100 – 124 OR 5.6-6.9	$\geq 125$ OR $> 7.0$
HbA1c (%)	$\leq 6.1$	6.2 – 6.9	$\geq 7.0$
Daily average (previous week) insulin (IU/kg/day)	---	0.01 – 0.24	$\geq 0.25$
Stimulated C-peptide (ng/mL) 	$\geq 0.9^*$	0.3 – 0.89	$< 0.3^{\#}$

1: C-peptide level in the blood sample taken 90 min after drinking the mixed meal. \*: If fasting C-peptide is  $\geq 0.9$  ng/mL, then the stimulated C-peptide level is assumed to be  $\geq 0.9$  ng/mL. #: If stimulated C-peptide is  $< 0.3$  ng/mL, then an overall score of 0 is awarded

#### 14.7. APPENDIX 7 – SAMPLE DIARY CARD

Clinical Trial REP0112	PATIENT DIARY CARD						PATIENT No.    
Sponsor: Dompé s.p.a.							

Please report in the table below your blood glucose (fingerstick) for 14 days before the planned follow-up visit. You are required to report at least one value taken after an overnight fast (or anyway before breakfast) and one value taken within 2 hours after one of the two meals. Also, please report the total amount of insulin you have taken each day.
 
Please add the date as day/month/year (example 25/07/2012 for 25 July 2012) and the time as 24 hours clock (example 9.35 in the morning, 21.35 in the afternoon). Please enter the information requested with indelible ink.
							
Day	Breakfast glucose		Lunch glucose		Dinner glucose		Daily Insulin
	Time	Value Before	Time	Value After	Time	Value After	
Monday - date:							
Tuesday - date:							
Wednesday - date:							
Thursday - date:							
Friday - date:							
Saturday - date:							
Sunday - date:							

Investigator's signature: \_\_\_\_\_ date: \_\_\_\_\_

## GLOSSARY OF ABBREVIATIONS

ADIR	Average Daily Insulin Requirements
AE	Adverse Event
ALT	Alanine Aminotransferase
APTT	Activated Partial Thromboplastin Time
AST	Aspartate Aminotransferase
AUC	Area Under the Curve
BP	Blood Pressure
CLcr	Calculated Creatinine Clearance (Cockcroft - Gault formula)
CRF	Case Report Form
CRO	Contract research organization
CRP	C-reactive Protein
DMC	Data Monitoring Committee
HbA1c	Glycated hemoglobin
HR	Heart Rate
Kg	Kilogram
IAT	Islet Auto-Transplantation
IEQ	Islet Equivalent
INR	International Normalized Ratio
ITT	Intent to Treat
MMTT	Mixed Meal Tolerance Test
NSAID	Non Steroidal Anti-inflammatory Drug
PK	Pharmacokinetic
PP	Per Protocol
PTT	Partial Thromboplastin Time
SAE	Serious Adverse Event
SAP	Statistical Analysis Plan
TEAE	Treatment emergent adverse event
ULN	Upper Limit of Normal
XDP	Fibrin Degradation Products

REP0112

Statistical Analysis Plan

## 1 INTRODUCTION

### 1.1 General

This statistical analysis plan (SAP) describes the statistical methods to be used during the analysis and reporting of data collected under Dompé farmaceutici S.p.A (Dompé) Protocol REP0112.

The SAP will be finalized and approved by the sponsor in addition to the Project Manager and Statistician of the contract research organization appointed by Dompé prior to database lock.

### 1.2 Changes From Protocol

Not pertinent.

### 1.3 Changes From Previous Versions of SAP

Not pertinent.

## 2 STUDY OBJECTIVES

The objective of this clinical trial is to assess whether reparixin leads to improved transplant outcome as measured by the proportion of insulin-independent patients following islet auto-transplantation (IAT). The safety of reparixin in the specific clinical setting will also be evaluated.

## 3 STUDY DESIGN

### 3.1 Overview

The study will be a phase 2/3, multicenter, randomized, double-blind, placebo-controlled, parallel assignment pilot study.

The goal of this study is to reach a total of 100 adult patients who are randomized and receive IAT after total or completion pancreatectomy. Patients will be randomly (1:1) assigned to receive either reparixin [continuous intravenous infusion for 7 days (168 hours)], or matched placebo (control group), starting approximately 12 hours before islet infusion. The two groups will be balanced within each centre. All patients who are randomized and receive the investigational product (either reparixin or placebo) will be included in the intent to treat (ITT) analysis. Patients will be in the ITT analysis whether or not they receive IAT, because exclusions cannot be made for events occurring after randomization that could be influenced by the randomized assignment.

Recruitment will be competitive among the study sites, until the planned number of patients is enrolled. Competitive recruitment has been chosen to increase the speed of recruitment and to account for any difference in transplant rate among study sites. Each centre will enroll patients as rapidly as possible, up to a maximum of 40 patients (as per the randomization list).

Each patient will be involved in the study for at least a 7 day hospital stay during pancreatectomy followed by IAT, for all required measurements up to hospital discharge and for 2 post-transplant visits scheduled at Day 75 ± 14 days and Day 365 ± 14 days after the transplant.

### 3.2 Inclusion and Exclusion Criteria

To be eligible for inclusion into this study, each patient must fulfill ALL of the following inclusion criteria:

REP0112

Statistical Analysis Plan

1. Patients eligible for an IAT following total (or completion) pancreatectomy.
2. Ages  $\geq$  18 years.
3. Patients willing and able to comply with the protocol procedures for the duration of the study, including scheduled follow-up visits and examinations.
4. Patients who have given written informed consent, prior to any study-related procedure not part of normal medical care, with the understanding that consent may be withdrawn by the patient at any time without prejudice to their future medical care.

Patients who meet any of the following exclusion criteria are NOT eligible for participation in the study:

1. Recipients of a previous IAT (if completion pancreatectomy).
2. Patients undergoing total pancreatectomy due to either pancreatic cancer or pancreatic benign diseases other than chronic pancreatitis, including insulinomas, etc.
3. Patients with inadequate renal reserve as per calculated creatinine clearance (CLcr) < 60 mL/min according to the Cockcroft-Gault formula (1976).
4. Patients with hepatic dysfunction as defined by increased alanine aminotransferase/aspartate aminotransferase (ALT/AST) > 3 x upper limit of normal (ULN) **or** increased total bilirubin above the upper limit at local laboratory. Patients with Gilbert's syndrome (elevated unconjugated bilirubin levels in the absence of any evidence of hepatic or biliary tract disease) are not excluded.
5. Patients with a preoperative International Normalized Ratio (INR) > 1.5 or any known coagulopathy.
6. Hypersensitivity to:
  - a) ibuprofen or to more than one non steroidal anti-inflammatory drug (NSAID).
  - b) more than one medication belonging to the class of sulfonamides, such as sulfamethazine, sulfamethoxazole, sulfasalazine, nimesulide or celecoxib; hypersensitivity to sulphanilamide antibiotics alone (e.g. sulfamethoxazole) does not qualify for exclusion.
7. Concurrent sepsis (as per positive blood culture(s) and/or fever associated with other signs of systemic sepsis syndrome).
8. Treatment with systemic steroids in the 2 weeks prior to enrolment (except for the use of  $\leq$ 5 mg prednisone daily or equivalent dose of hydrocortisone, for physiological replacement only) or with any immune modulators in the 4 weeks prior to enrolment.
9. Patients with pre-existing diabetes or evidence of impaired  $\beta$ -cells function, based on pre-operative fasting blood glucose >115 mg/dL and/or a HbA1c > 6.5%, or requiring treatment with any anti-diabetic medication (e.g. insulin, metformin, etc) within the 2 weeks prior to enrolment.
10. Use of any investigational agent in the 4 weeks prior to enrolment, including any anti-cytokine/chemokine agents.
11. Pregnant or breast-feeding women; unwillingness to use effective contraceptive measures (females and males). (NB: pregnancy should be avoided in patients or partners during the first month after completing the treatment with the investigational product; no other specific warnings are described, considering the treatment course of the investigational product, its pharmacokinetic (PK) profile, and the lack of significant adverse effects on mating performance and fertility in animal studies).

REP0112

Statistical Analysis Plan

12. Patients with past or current history of alcohol abuse based on clinical history and/or past treatment for alcohol addiction.
13. Patients with evidence of pre-operative portal hypertension as per clinical history **and** abdominal/liver imaging by ultrasound techniques.

Sites will comply with any additional or more restrictive exclusion criteria locally accepted, as per centre practice.

### 3.3 Sample Size Considerations

The primary efficacy endpoint of the clinical trial is the proportion of insulin-independent patients following IAT at Day 365 ± 14 days after the transplant.

In the following considerations, statistical significance for this endpoint will be achieved if the Pearson Chi-square statistic yields a two sided p-value less than 0.05. The corresponding false positive error rate is (one-sided) 0.025. In addition, a 95% confidence interval for the difference of success (failure) rates between the reparixin and placebo groups will be provided based on the normal distribution approximation to the standardized difference in estimated success rates.

Based on published data from a retrospective series (Sutherland, 2012), it appears that the likelihood of achieving insulin independence at 12 month follow-up in the placebo control arm depends upon the number of IEQ/kg, with patients categorized in three groups:

- <2500 IEQ/kg: 13% insulin independence
- 2500-5000 IEQ/kg: 23% insulin independence
- >5000 IEQ/kg: 55% insulin independence

In their overall series, the yields were <2500 IEQ/kg in 36%, 2500-5000 IEQ/kg in 39% and >5000 IEQ/kg in 24% of patients. In the more recent series of 217 patients receiving IAT from 2006 to 2011, corresponding yields were <2500 IEQ/kg in 34%, 2500-5000 IEQ/kg in 42%, and >5000 IEQ/kg in 24%.

Initial focus is placed on the cohort that is in the range 2500-5000 IEQ/kg, since these participants will be the largest fraction of enrollees. It is anticipated that the percentage of such patients achieving insulin independence will be increased from 23% in the placebo control arm to 55% in the reparixin arm. Using standard statistical formulas based on the approximation of the binomial distribution by the normal distribution, the sample size of 44 patients per arm provides 90% power to detect a 23% versus 55% true difference when using a Pearson Chi-square statistic having the traditional (one-sided) 2.5% false positive error rate. Even accounting for the discreteness, the power should be in the 87% to 90% range. Furthermore, with 44 patients per arm, statistical significance (i.e., one-sided  $p=0.025$ ) will be obtained if the estimated difference is 22.7% (10/44) versus 43.2% (19/44), which is an estimated 20.5% increase in percentage of patients achieving insulin independence. Hence, with 44 patients per arm, statistical significance is achieved with an estimated effect size that is clinically meaningful.

Even though the largest percentage of patients will be in the cohort receiving IEQ/kg in the range 2500-5000 IEQ/kg, the trial will also enroll participants in two additional strata: <2500 IEQ/kg and >5000 IEQ/kg. As noted above, we are presuming the middle strata would have an increase from 23% to 55% in percentage of patients achieving insulin independence. This is an odds ratio higher than 4. If we have an odds ratio of approximately 4.3 to 4.5 in the other 2 strata and if approximately 1/2 of the patients would be from the 2500-5000 IEQ/kg stratum, then only a modest increase of about 12 additional patients beyond the 88 patient sample size would be needed to maintain the statistical power of the trial. An increase in success rate from 13% to

REP0112

Statistical Analysis Plan

40% in the <2500 IEQ/kg stratum would be an odds ratio of 4.4 and an increase in success rate from 55% to 84% in the >5000 IEQ/kg stratum would be an odds ratio of 4.3.

Based on these considerations, it is planned to enroll 100 patients in this trial who receive IAT, with the expectation that there will be approximately 5 others who do not receive IAT. Under such a plan, the trial would not be overpowered even if all participants were in the 2500-5000 IEQ/kg stratum since statistical significance (i.e., one-sided  $p=0.025$ ) would be obtained with 52 patients per arm if the estimated difference is 23.1% (12/52) versus 42.3% (22/52), which is an estimated clinically significant 19.2% increase in percentage of patients achieving insulin independence.

The sample size of 100 to 105 patients also provides high statistical power for the key secondary endpoint, C-peptide area under the curve (AUC) (mixed meal tolerance test [MMTT]) normalized by IEQ/kg. Based on preliminary data reported from the ongoing pilot trial, Month 1 post transplant means and standard deviations for this endpoint are  $1.92 \pm 1.62$  in the reparixin group and  $0.44 \pm 0.04$  in the control group. With 52 patients in each treatment group, the trial will have greater than 95% power to detect a difference in means of at least 1.48 (the difference between a treated mean of 1.92 and a control mean of 0.44) assuming that the common standard deviation is 1.37 and using an 0.0025 two-sided significance level.

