## 9. STATISTICAL ISSUES

### 9.1. SAMPLE SIZE

The primary efficacy endpoint of the clinical trial will be the proportion of insulin-independent patients following IAT over the time frame: day 365±14 after the transplant.

In the following considerations, statistical significance for this endpoint will be achieved if the Pearson Chi-Square Statistic yields a two sided p-value less than 0.05. The corresponding false positive error rate is (one-sided) 0.025. In addition, 95% confidence interval for the difference of success (failure) rates between the reparixin and placebo groups will be provided, based on the normal distribution approximation to the standardized difference in estimated success rates.

Based on published data from a retrospective series (*Sutherland, 2012*), it appears that the likelihood of achieving insulin independence at 12 month follow-up in the placebo control arm depends upon the number of IEQ/kg, with patients categorized in three groups:

- < 2500 IEQ/kg: 13% insulin independence
- 2500-5000 IEQ/kg: 23% insulin independence
- > 5000 IEQ/kg: 55% insulin independence

In the overall series, the yields were <2500 IEQ/kg in 36%, 2500-5000 IEQ/kg in 39% and > 5000 IEQ/kg in 24% of patients. In the more recent series of 217 patients receiving IAT from 2006 to 2011, corresponding yields were <2500 IEQ/kg in 34%, 2500-5000 IEQ/kg in 42% and > 5000 IEQ/kg in 24%.

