#### Primary Analysis

The proportion of insulin-independent patients will be compared between treatment groups using the Cochran-Mantel-Haenszel test stratified by baseline IEQ/kg (<2500 IEQ/kg, 2500-5000 IEQ/kg, and >5000 IEQ/kg). The hypothesis to be tested is:

Null Hypothesis,  $H_0$ :  $p_{\text{reparixin}} \leq p_{\text{placebo}}$  for all baseline IEQ/kg strata

Alternative Hypothesis,  $H_A$ :  $p_{\text{reparixin}} > p_{\text{placebo}}$  for at least one baseline IEQ/kg strata

The significance level used for statistical testing will be 2.5% and a one-sided test will be used. The 95% confidence interval for treatment proportions and the one-sided 95% confidence interval for the difference in treatment proportion between reparixin and placebo will be produced.

As a sensitivity analysis, the primary analysis will be repeated for the ITT population, dropping from the analysis any site with >20% of subjects not having data for the primary endpoint recorded; subjects will be considered to not have data recorded for the primary endpoint if they have discontinued the study prior to attending the Day 365 visit or if they have attended the Day 365 visit but did not have the primary endpoint recorded. The intent is to examine the sensitivity of the primary analysis to sites lacking a reasonable number of patients with data captured for the primary endpoint.

The relevance of the treatment-by-site interaction will be investigated using a logistic regression model which will include the main effect of treatment and IEQ/kg infused at IAT (<2500 IEQ/kg,

REP0112

Statistical Analysis Plan

2500-5000 IEQ/kg, and >5000 IEQ/kg) and site as covariates. The analysis variable for treatment will be coded such that the reference treatment is placebo, the analysis variables for IEQ/kg infused at IAT will be coded such that the reference group is <2500 IEQ/kg, and the analysis variables for site will be coded such that the reference site is Site 1. The treatment-by-site interaction will be examined, and if not significant at the 0.10  $\alpha$ -level, will be removed from the model. The hypothesis to be examined is:

Null Hypothesis,  $H_0$ :  $\beta_{\text{treatment}} \leq 0$

Alternative Hypothesis,  $H_A$ :  $\beta_{\text{treatment}} > 0$

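### The primary test is stratified by IEQ/kg, but the only method stated for the interval on the risk difference is unstratified; the SAP should name a Mantel-Haenszel difference and interval to go with the test (minor)

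*SAP*

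**What the plan says.** **Test.** SAP 7.5.1 (Primary Analysis) compares the arms "using the Cochran-Mantel-Haenszel test stratified by baseline IEQ/kg", with cut-points at 2500 and 5000 IEQ/kg. On the level: "The significance level used for statistical testing will be 2.5% and a one-sided test will be used". Protocol 9.4.2 also stratifies its chi-square by these groups.

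**Interval.** The same SAP section says that a "one-sided 95% confidence interval for the difference in treatment proportion between reparixin and placebo will be produced". It gives no formula, weights or strata and does not refer back to 3.3. The one description of a method is in SAP 3.3, where the 95% interval "will be provided based on the normal distribution approximation to the standardized difference in estimated success rates"; Protocol 9.1 has the same description. In both places it follows a statement about an unstratified test: "statistical significance for this endpoint will be achieved if the Pearson Chi-square statistic yields a two sided p-value less than 0.05".

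**Other effect estimates.** SAP 7.5.1 also plans a logistic regression on treatment, IEQ/kg group and site, reporting an odds ratio with a one-sided 95% interval. The tables list it as a sensitivity analysis, for both the ITT and PP populations. Results by arm within each stratum are to be tabulated.

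**Parallel analysis.** Addendum 3.2.2.3 repeats the CMH approach for HbA1c ≤6.5%. Its table shell ties CMH to the p-value and puts one difference and interval on the Overall row.

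**The concern.** The plan's placebo rates are 13%, 23% and 55% across the strata, so IEQ/kg is strongly prognostic. Randomization is blocked within centre, not by IEQ/kg, so chance imbalance between the arms is expected. The CMH test removes both sources of variation. A crude difference with its normal-approximation standard error keeps both. If the interval follows SAP 3.3, a significant primary test can appear beside an interval that includes zero, or the reverse, and some available precision is lost. This is separate from whether the interval is one-sided or two-sided: it remains when the levels match.

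**Working it through.** **Inputs (SAP 3.3).** Placebo rates 13/23/55%; reparixin rates 40/55/84%; stratum mix 34/42/24% (the 2006-2011 series); 100 patients receiving IAT, taken as 50 per arm.

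**1. The plan's own figure.** SAP 3.3 says that "the sample size of 44 patients per arm provides 90% power to detect a 23% versus 55% true difference". The normal approximation gives 88.2% with pooled variance and 90.3% with unpooled variance; exact binomial power of the Pearson test is 88.8%. The figure reproduces. The documents give no figure for the interval.

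**2. Expected standard errors.**

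- Overall placebo rate: 0.34×0.13 + 0.42×0.23 + 0.24×0.55 = 0.273.
- Overall reparixin rate: 0.34×0.40 + 0.42×0.55 + 0.24×0.84 = 0.569. The difference is 0.296.
- Crude SE = √[(0.273×0.727 + 0.569×0.431)/50] = 0.0942; 95% half-width 18.5 points.
- Stratified SE = √[Σ w(p₀q₀ + p₁q₁)/50] = √[(0.34×0.3531 + 0.42×0.4246 + 0.24×0.3819)/50] = 0.0883; half-width 17.3 points.
- Ratio 0.0942/0.0883 = 1.067. With an assumed 25/50/25% mix it is 1.062.

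**3. An example with balanced strata.** Take 17/21/12 patients per arm; placebo successes 2/5/7 (14/50); reparixin successes 3/10/10 (23/50).

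- CMH: observed minus expected = 0.5 + 2.5 + 1.5 = 4.5; variance = 1.098 + 2.470 + 1.293 = 4.861; z = 4.5/√4.861 = 2.04; one-sided p = 0.0206. The test succeeds.
- Crude: difference 0.18; SE = √[(0.28×0.72 + 0.46×0.54)/50] = 0.0949; two-sided 95% interval -0.6 to 36.6 points, which includes zero.
- Mantel-Haenszel with Sato variance: SE² = (Δ·ΣP + ΣQ)/(Σw)². In each stratum, with subscript 1 for reparixin and 0 for placebo:
  - w = n₁n₀/N
  - P = [n₁²x₀ - n₀²x₁ + n₁n₀(n₀-n₁)/2]/N²
  - Q = [x₁(n₀-x₀) + x₀(n₁-x₁)]/(2N)
  - Here Δ = 0.18, Σw = 25, ΣP = -2.25 and ΣQ = 4.966, so SE = √[(-0.405 + 4.966)/625] = 0.0854. The interval is 1.3 to 34.7 points, which excludes zero.

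The two point estimates are identical, so the contradiction comes from the variance alone.

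**4. How often the test and interval disagree.** These are simulated trials (100,000 to 200,000 per scenario), CMH at one-sided 2.5% against a two-sided 95% interval, mix 34/42/24%.

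| Scenario | Crude: test significant, zero inside | Crude: reverse | Crude: total | Mantel-Haenszel/Sato: total |
|---|---|---|---|---|
| Planned effect | 4.4-4.6% | 1.7-1.8% | 6.1-6.4% | 0.9% |
| Common odds ratio 3.0 or 2.5 | about 8% | about 4% | about 11-12% | about 2% |
| No effect | 0.8% | 1.1% | 1.9% | 0.3% |

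Mean full interval width at the planned effect is 0.365 crude and 0.346 Mantel-Haenszel, so the crude interval is 0.365/0.346 = 1.055 times as wide. CMH power there is about 90%. Both differences average 29.6 points at the planned effect, 22.0 at odds ratio 3.0 and 18.0 at 2.5.

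**The case against.** Several counter-arguments have force.

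- **SAP 7.5.1 does not say crude.** The normal-approximation sentence belongs to the sample-size considerations and accompanies a test that 7.5.1 does not use. A reader might infer that the SAP commits to the crude interval. The text supports only that it is the one method described and that the governing section names none. Either way, the method has to be stated in 7.5.1.
- **An adjusted estimate is planned.** A reader might infer that the primary endpoint has no IEQ/kg-adjusted effect estimate. It has one: the logistic odds ratio. But that is a sensitivity analysis on the odds scale with site in the model, so it is not the interval that belongs with the CMH p-value.
- **The two summaries answer different questions.** This is also tempting, but the plan's figures do not support it. The planned stratum differences are 27, 32 and 29 points, and the crude and stratified estimates have the same average. The gap is one of efficiency.
- **The disagreement rates assume a two-sided 95% interval.** SAP 7.5.1 asks for a one-sided 95% interval. Computed crudely at that level, a significant test with zero inside falls to 1.4% of trials at the planned effect and the reverse rises to 3.9%, the latter mainly because the level does not match the test. That mismatch is a separate matter.
- **The fix is not free or complete.** ITT patients without IAT have no infused IEQ/kg, so a stratified estimate drops them unless a rule places them. The CMH test already has this gap. A Mantel-Haenszel interval also leaves some disagreement: about 1-2% with Sato variance, somewhat more with Greenland-Robins variance (1.5% at the planned effect).

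**Conclusion.** The point holds as a minor one. The primary p-value uses the IEQ/kg strata; the only interval method stated does not. At the plan's own rates this costs about 5-7% in interval width (roughly 1.2 points of half-width). A crude two-sided 95% interval would disagree with the primary test in about 6% of trials at the planned effect and 11-12% at a common odds ratio of 3.0 or 2.5. Nothing here affects the type I error or power of the CMH test, which alone decides significance.

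The figures assume 50 patients per arm, all with a known stratum, the published mix and placebo rates, and an interval level that matches the test. The copy read lacks the body of Addendum 3.2.1 (Primary Variable) and some addendum table shells. If an interval method is set out there, SAP 7.5.1 need only refer to it.

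**What to change.** In SAP 7.5.1, and in the matching sentence of 3.3, define the primary effect estimate as the Mantel-Haenszel risk difference over the CMH strata, with a Sato (or stratified Newcombe) 95% interval at the level matching the one-sided 2.5% test. Keep the crude difference in the table as descriptive. Use the same pairing for the addendum's CMH analysis of HbA1c ≤6.5%.

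Add one rule, applied identically in the test and the estimate, for ITT patients without IAT (about five expected), for example assigning them to the lowest stratum, so that they are not dropped.

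The cost is a sentence or two in the SAP and a standard software option. No new data or patients are needed. The one small burden is the stratum rule, which the CMH test needs anyway.
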